10.2. Plasma PK Parameters

It should be noted that the handling of BLQ concentration values for the calculation of $t_{1/2}$ and the AUC parameters with the software package differs from the approach described above (Section 10.1) for the summary of plasma concentrations. For the calculation of these parameters, BLQ values will be set equal to zero with the exception of BLQ values bounded by quantifiable values. BLQ values between quantifiable concentrations will be ignored (i.e., treated as missing values) for the calculation of these parameters.

11. SAFETY

Results will be presented using the safety analysis set, as described in Section 6.2.1.1.

11.1. Adverse Events

Adverse events are recorded in the electronic case report form (eCRF). Each AE will be coded to a SOC and PT using MedDRA (version 24.0).

A treatment-emergent adverse event (TEAE) is an adverse event not present prior to the initiation of study drug dosing or is an already present event that worsens either in intensity or frequency following the initiation of study drug dosing and also occurs on or before the last dose of study drug. Investigators will be asked to respond "Yes" or "No" on the CRF as to whether the AE started after the subject took the first dose of study drug. An AE with a response of "Yes", and that occurs on or before the last dose of study drug, will be classified as a TEAE. If the investigator's response is missing on the CRF, then the treatment emergent status will be derived based on the AE onset date and time relative to the date and time of the subject's first and last dose of study drug. If the AE onset date and time are unknown, it will be assumed that the AE is a TEAE. If the AE onset time is unknown but the AE onset date is the same date as the first dose of study drug, it will be assumed that the AE is a TEAE. Adverse events that occur after the last dose of study drug but on or before the last dose plus 21 days will be considered post-treatment emergent (post-TEAEs). Adverse events with an onset date after the last dose plus 21 days will not be considered treatment emergent (non-TEAEs).

TEAEs, post-TEAEs, and non-TEAEs categorized by MedDRA SOC and/or PT, will be summarized in frequency tables. The frequency tables will include the number and percentage of unique subjects experiencing each event one or more times.

Two similar frequency tables will be generated for TEAEs – one including both SOC and PT (each sorted in alphabetical order), and one including PT only, with PTs sorted in order of decreasing frequency of subjects reporting the PT. Post-TEAEs and non-TEAEs will be summarized by SOC and PT only (each in alphabetical order).

An overall summary table will be provided which summarizes the number and percentage of unique subjects with any TEAE, any TEAE leading to study discontinuation, any serious TEAE, and any TEAE resulting in death. The summary table will also include the frequency distribution of the maximum TEAE intensity (mild, moderate, severe). A subject with more than one event coded to the same PT will be classified according to the most severe event.

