10. ADVERSE EVENTS

All AEs, whether observed by the investigator, reported by the subject, noted from laboratory findings, or by other means, will be recorded from the time the subject has signed the ICF until the subject's final study visit.

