12.8. Safety Data

TEAEs, categorized by system organ class (SOC) and/or preferred term as defined by MedDRA, will be summarized. A TEAE is defined as any AE that occurs after the first dose of study drug. Any AE that occurred before the first dose of study drug will be considered a pretreatment AE. The TEAE tables will include the number and percentage of unique subjects experiencing each event.

Clinical laboratory data, vital sign measurements, ECG data, and other safety data will be summarized by timepoint (as appropriate) with descriptive statistics.

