11.1.1. Adverse Events Resulting in Premature Discontinuation from Study

Summary tables of TEAEs resulting in early discontinuation from the study will be presented. The number and percentage of subjects with a TEAE resulting in study discontinuation will be presented by PT within SOC (presented in the same method as the analogous primary TEAE table). More than one AE can contribute to study discontinuation per subject. The first line of the table will display the number and percentage of subjects with at least one TEAE leading to study discontinuation.

A listing of TEAEs resulting in premature study discontinuation will be provided which includes subject ID, treatment, study day of the discontinuation, and other relevant information from the AE eCRF.

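### SAP 11.1 closes the TEAE window at the last dose, which protocol 12.8 does not, so AEs that start after the last dose leave the overall, intensity and discontinuation summaries

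*SAP*

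**What the plan says.** Protocol 12.8 gives a definition that is open at the end: "A TEAE is defined as any AE that occurs after the first dose of study drug". Under protocol section 10, AEs "will be recorded from the time the subject has signed the ICF until the" final study visit, which is planned for Day 35 with a window of +7 days.

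SAP 11.1 narrows this. An event must be new or worsen "following the initiation of study drug dosing and also occurs on or before the last dose of study drug". The operational rule repeats the bound: an AE that the investigator marks as having started after the first dose, "and that occurs on or before the last dose of study drug, will be classified as a TEAE". AEs with later onset become post-TEAEs up to 21 days after the last dose, and non-TEAEs beyond that.

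The outputs then differ by class. "Post-TEAEs and non-TEAEs will be summarized by SOC and PT only". The overall summary table in SAP 11.1 (any TEAE, TEAE leading to study discontinuation, serious TEAE, fatal TEAE) and its maximum-intensity distribution are defined on TEAEs alone. So is SAP 11.1.1: "Summary tables of TEAEs resulting in early discontinuation from the study will be presented", with a matching listing. In SAP 11.1.2 the table and listing of serious AEs (SAEs) are not limited to TEAEs, but the separate listing of deaths is.

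**The concern.** Safety and tolerability is the first-listed objective, and follow-up after dosing is longer than dosing itself. The two documents use one term for two different windows, and the narrower one drives the main AE outputs.

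The discontinuation output is the most exposed. SAP 8.1 counts study completion up to Day 35, so a subject can finish dosing and still leave the study during follow-up. If an AE that began after the last dose is the reason, SAP 11.1.1 as worded does not show it. The same holds for a subject who stops dosing early and then withdraws because of an AE that began after that subject's own last dose.

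For AEs that start after the last dose, no planned summary table gives intensity or names the preferred term that led to discontinuation.

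**Working it through.** The documents give no figure on this point to reproduce. The check compares the texts and then does date arithmetic on the planned schedule.

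**1. Does the closing bound apply to all AEs?** The definition sentence alone could be read as limiting only events that were already present and worsened. The operational rule in SAP 11.1 excludes that reading, because it puts the same bound on every AE with a Yes response. Later onsets are also expressly assigned to the other two classes.

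**2. Window for a subject who takes all planned doses.** Inputs are the first dose on Day 1 at about 1900 and the last on Day 14 at about 1900 (protocol section 6), with the final visit on Day 35, taken at 1900.

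- SAP window: Day 1 1900 to Day 14 1900 = 13 days × 24 = 312 h.
- Protocol window: Day 1 1900 to Day 35 1900 = 34 days × 24 = 816 h.
- Difference: 816 − 312 = 504 h (21 days), which matches the 504-hour label for Day 35 in protocol Table 1.
- Shares: 312/816 = 38.2% inside the SAP window; 504/816 = 61.8% outside it.

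**3. Late final visit (+7 days, Day 42).** The protocol window is 41 days (984 h), of which 28/41 = 68.3% is outside the SAP window. Last dose plus 21 days falls on Day 35. SAP 11.1 words this second bound by onset date, so non-TEAEs begin on Day 36. To Day 42 at 1900 that is 6 × 24 + 19 = 163 h. Counted by clock time from Day 35 at 1900, it is 168 h.

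**4. Direction of the effect, taking the closing bound alone.**

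- Counts of subjects with any TEAE, a serious TEAE, a fatal TEAE or a TEAE leading to discontinuation can only fall or stay the same.
- Each subject's own maximum intensity can only fall or stay the same. Category counts need not. Take a subject with a mild AE on Day 5 and a severe AE on Day 16. The protocol definition counts the subject as severe; the SAP counts the subject as mild. The severe count falls by one and the mild count rises by one.

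**5. Sensitivity.** Assume 12 subjects in the safety set; the documents say approximately 12 will be enrolled. If k subjects have only AEs that start after the last dose, TEAE incidence falls by k/12:

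| k | Fall in TEAE incidence (percentage points) |
|---|---|
| 1 | 8.3 |
| 2 | 16.7 |
| 3 | 25.0 |

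The documents cannot tell us k.

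**6. The boundary itself.** When the investigator's response is missing, "the treatment emergent status will be derived based on the AE onset date and time relative to the date and time" of the first and last dose. SAP 11.1 also says what to do when the onset time is unknown on the first-dose date. It gives no such rule for the last-dose date.

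**The case against.** The best case for the SAP is that separating on-dosing from post-dosing events is a sensible display in a study with 14 days of dosing. Adding 21 to 28 off-drug days to the headline rate is not obviously better. Protocol section 12 also leaves the detail of data summaries to the SAP. The first part stands, and it is why the remedy should keep the split. The second does not settle the matter, because protocol 12.8 states the TEAE definition itself and does not defer it.

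Much of the information also survives:

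- Post-TEAEs and non-TEAEs keep tables by system organ class and preferred term.
- SAEs of any timing, including deaths, keep a table and a listing (SAP 11.1.2).
- Disposition reports reasons for discontinuation (SAP 8.1).
- AEs with unknown onset date and time default to TEAE (SAP 11.1).

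All of this stands and limits the point.

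A reader might go further in three ways that the text does not support.

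- One might say that every AE beginning after Day 14 is lost from the TEAE outputs. SAP 6.5.1.1 imputes some partial dates to the first-dose date, so some of these AEs may still be classed as TEAEs.
- One might say that the SAP leaves date against clock time open throughout. Protocol 9.6 records exact dosing times, protocol 10.4 records onset dates and times, and the SAP's fallback rule compares date and time. The real gap is only an AE on the last-dose date with no onset time.
- One might say that the change went undeclared. SAP section 12 shows only a heading in the available text, so this cannot be judged.

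**Conclusion.** The two definitions conflict, and the conflict changes outputs as well as labels. As written, the SAP omits AEs that start after the last dose from the overall TEAE summary, the maximum-intensity distribution and the SAP 11.1.1 tables and listing. What is mainly lost is the intensity of non-serious AEs with onset after the last dose, and the preferred term when such an AE leads to discontinuation.

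For a subject who completes dosing on schedule, the TEAE window is 13 of 34 days. It would be wrong to infer that 61.8% of AEs are lost: that figure is a share of time, and AEs need not be spread evenly over it. It would also be wrong to infer that every row of the intensity table can only go down, since counts in lower categories may rise. The figure of 8.3 points per affected subject rests on an assumed safety set of 12.

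The point lies between minor and should-fix.

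**What to change.** Reconcile SAP 11.1 with protocol 12.8. At minimum, keep the on-dosing and post-dosing split and make three changes:

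- In the overall summary, add any-event, maximum-intensity and leading-to-discontinuation rows for post-TEAEs and non-TEAEs, or for all AEs after the first dose.
- Base the SAP 11.1.1 tables and listing on all AEs after the first dose.
- State how an AE on the last-dose date with no onset time is classified.

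Restoring the protocol window as the headline TEAE definition would also resolve the conflict. It is the more debatable choice, because it puts off-drug time into the main rate.

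The cost is SAP wording, some reprogramming and a few extra rows, with no new data. Some off-drug events will appear in the added rows, and the split identifies them.

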10.4. Recording Adverse Events

For enrolled subjects, each AE will be listed as a separate entry on an AE eCRF. Screen failure subjects will have AE information noted in the source documentation. The investigator (or designee) will provide information on dates and times of onset and resolution, intensity, seriousness, frequency, action(s) taken, changes in study drug usage, relationship to study drug, and outcome.

The following categories of medical events that could occur during participation in a clinical study must be reported within 24 hours to NBI or its designee:

- SAE, including death (Section 10.6).
- Pregnancy (Section 10.7).
- Events of suicidal behavior or suicidal ideation type 4 (active suicidal ideation with some intent to act, without specific plan) or type 5 (active suicidal ideation with specific plan and intent) based on the C-SSRS.

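### SAP 11.1 counts worsening of an existing event as treatment-emergent, but its classification rule uses onset only, so a pre-dose AE that worsens under the same eCRF entry is not classified as a TEAE

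*SAP*

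**What the plan says.** SAP 11.1 gives a TEAE definition with two limbs. The first is an event absent before dosing began. The second is "an already present event that worsens either in intensity or frequency following the initiation of study drug dosing". Both are limited to events on or before the last dose.

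The same section then says how the class is assigned:

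- The investigator gives a Yes or No answer "as to whether the AE started after the subject took the first dose of study drug". Any event marked Yes "and that occurs on or before the last dose of study drug, will be classified as a TEAE".
- If that answer is missing, "the treatment emergent status will be derived based on the AE onset date and time relative to the date and time"; the reference times are those of first and last dosing.
- "If the AE onset date and time are unknown, it will be assumed that the AE is a TEAE". An AE dated on the day of first dose with no time is also assumed to be a TEAE.
- AEs after the last dose and up to 21 days later are post-TEAEs. AEs with onset later than that are non-TEAEs.

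The protocol adds four relevant points:

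- Section 10: AEs "will be recorded from the time the subject has signed the ICF", so the AE form can hold events that began before dosing.
- Section 10.1: worsening of a condition present at study start is an AE. A persistent pre-dose condition also becomes one if it unexpectedly progresses or becomes more severe after drug administration.
- Section 10.4: "each AE will be listed as a separate entry on an AE eCRF". It does not say whether a change in intensity opens a new entry, or what start date that entry would carry.
- Section 12.8: a TEAE is any AE occurring after the first dose, with no worsening limb. Earlier AEs are pretreatment.

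**The concern.** The definition and the rule that is meant to apply it do not match. Worsening is in the definition, but no classification step asks about it, derives it or names a variable for it. A programmer following the written steps would leave a worsened pre-dose AE out of the TEAE class. A programmer following the definition would have to devise a rule with the data in view.

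Safety and tolerability is the first-listed objective, and the study has no control arm. Worsening of something already present is one of the signs of a possible drug effect that such a study can show. Several outputs are restricted to TEAEs: the SOC and preferred-term tables, the overall summary, the maximum-intensity distribution, and the table and listing of events leading to discontinuation. Protocol 8.10.1 requires withdrawal when the type, frequency or severity of an AE becomes intolerable. A pre-dose AE that worsened to that point could end a subject's participation and still be absent from the discontinuation outputs.

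There is a smaller, related weakness. Dates are consulted only when the CRF answer is missing, so as written a mistaken No prevails over a recorded onset after the first dose.

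**Working it through.** The plan gives no figure to reproduce. The check traces the SAP 11.1 rule through each way an event on or before the last dose could be recorded.

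| Case | How it is recorded | CRF answer | Class under the written rule | Meets the SAP definition? |
|---|---|---|---|---|
| a | Onset after first dose | Yes | TEAE | Yes |
| b | Baseline condition worsens; new AE entry dated at the worsening | Yes | TEAE | Yes |
| c | AE with onset between consent and first dose; worsens on drug under the same entry | No | Not classified as TEAE | Yes |
| d | As c, CRF answer missing, onset known | Missing | Onset-based derivation: not TEAE | Yes |
| e | CRF answer missing, onset unknown | Missing | Assumed TEAE | Cannot be judged |

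The rule and the definition part company in cases c and d. Neither case can move to another class: a post-TEAE must occur after the last dose, and a non-TEAE needs onset more than 21 days after it. Protocol 12.8 would call these events pretreatment AEs, but the SAP plans no frequency table for that class. The SAE tables in SAP 11.1.2 are not restricted to TEAEs, so a serious event in case c or d still appears there.

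Opportunity for cases c and d: screening can start on Day -28, and SAP 6.4.1 has no Day 0. Day -28 to Day -1 therefore gives up to 28 days in which an AE can be recorded before first dose.

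Size, taking the planned enrolment of about 12 as the denominator and k as the number of subjects whose only TEAE is lost:

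- Formula: loss in overall TEAE incidence = k/12.
- k = 0: 0/12 = 0 points.
- k = 1: 1/12 = 8.3 points.
- k = 2: 2/12 = 16.7 points.

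The values of k are illustrative, since the documents give no basis for choosing one. If the subject has another TEAE, overall incidence does not change. The row for the lost preferred term falls by 1/12, unless that subject has another TEAE under the same term, and the subject's maximum intensity may be understated.

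**The case against.** The best case for the plan has five parts.

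- **Worsening is an AE in its own right under protocol 10.1.** A medical-history or CAH-related condition that worsens on drug can be entered as a new AE, answered Yes and counted (case b). This stands, and it rules out the broader inference a reader might draw, that all worsened events vanish from every TEAE table. It does not clearly cover an AE already on the form, because section 10.4 does not say that a change in intensity opens a new entry.
- **The SAP never says that No excludes.** Yes is written as sufficient, and the definition still stands. This is correct as a reading, so it would go too far to say that the SAP expressly excludes these events. But no sentence places a No event that worsened, and the missing-answer fallback also uses onset alone.
- **eCRF completion instructions may settle the recording practice.** They may; they are not among the documents. A definite downward bias in TEAE incidence therefore cannot be asserted, only a conditional one.
- **Protocol 11.2 already provides source verification, logic checks on dates, manual review and queries.** These may catch a mistaken No. They would not catch case c, where No is truthful and the dates agree with it.
- **Few such events may arise.** Recent significant illness and acute or unstable findings are exclusions, and eligibility is updated on Day 1. This makes a large number less likely but does not remove the mismatch.

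**Conclusion.** The concern holds in a limited form. SAP 11.1 includes worsening in its TEAE definition and gives no rule that captures it. A non-serious AE recorded before first dose that worsens on drug under the same entry is not classified as a TEAE and falls in no planned AE frequency table. A serious one appears only in the SAE outputs.

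The size is 8.3 percentage points of TEAE incidence per subject whose only TEAE is lost, assuming 12 subjects in the safety analysis set. The number of such subjects is unknown and may be zero. The result rests on two assumptions: that the rule is applied as written, and that sites keep a worsening AE under its original entry. If sites open a new entry at the worsening, nothing is lost.

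This is more than missing detail, because the stated steps fail to carry out the SAP's own definition. Where onset is uncertain the SAP assumes a TEAE, whereas here the gap works in the opposite direction. That suggests an oversight, though the documents do not say so. The repair is cheap and should be made.

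**What to change.** 1. Amend SAP 11.1 along these lines: *An AE is a TEAE if, after the first dose and on or before the last dose of study drug, it starts, or an AE with earlier onset increases in intensity or frequency.* Leave the post-TEAE and non-TEAE windows and the unknown-onset defaults as they are. The last-dose limit must stay, since without it the TEAE class would overlap the other two.
2. Instruct sites to open a new AE record dated at the worsening. If entries can no longer be changed that way, review every No AE ongoing at first dose for worsening before lock.
3. Derive status from recorded onset date and time where available. Keep the CRF Yes or No as a cross-check, and query disagreements before lock.
4. Reconcile the definition with protocol 12.8, which has no worsening limb, and state the difference in SAP 12 if it is intended.

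If the database is already locked, SAP 2 requires the change to be described in the clinical study report.

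The cost is a short SAP edit, one eCRF completion instruction and one data check. The downside is a few more AE records and queries, and possibly a slightly higher TEAE count.

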11.1.1. Adverse Events Resulting in Premature Discontinuation from Study

Summary tables of TEAEs resulting in early discontinuation from the study will be presented. The number and percentage of subjects with a TEAE resulting in study discontinuation will be presented by PT within SOC (presented in the same method as the analogous primary TEAE table). More than one AE can contribute to study discontinuation per subject. The first line of the table will display the number and percentage of subjects with at least one TEAE leading to study discontinuation.

A listing of TEAEs resulting in premature study discontinuation will be provided which includes subject ID, treatment, study day of the discontinuation, and other relevant information from the AE eCRF.

11.1.2. Deaths and Other Serious Adverse Events

Summary tables of serious adverse events (SAEs) will be presented. The number and percentage of subjects with an SAE will be presented by PT within SOC (each sorted in alphabetical order). The first line of the table will display the number and percentage of subjects with at least one SAE.

Separate listings of SAEs and fatal TEAEs will also be provided. Each listing will include subject ID, treatment group, study day of the SAE or fatal TEAE, and any additional relevant information from the AE eCRF.

